#### 4.3 The Autoimmune Process of Type 1 diabetes

Development of autoimmune disorders is a result of breakdown in mechanisms that maintain unresponsiveness to self. Specifically, T1D is an automimmune disorder in which T cells are self-reactive or activated T cells that are activated against major antigenic components of pancreatic  $\beta$  cells are out of the control by the normal regulatory mechanisms. While these self-reactive T cells are under the control of peripheral regulatory mechanisms in healthy individuals, failure of control leads to the destruction of the  $\beta$  cells and consequent T1D. The autoimmune attack on pancreatic  $\beta$  cells is orchestrated by a variety of cells that produce cytokines and other toxic mediators. These self-reactive T cells work together with other lymphocytes and antigen-presenting cells to mediate this damage and have been shown in animal models to be important both in the early stages of diabetes development and in the final effector stages. They kill self-reactive T cells specific to self-antigens, which include  $\beta$  cell antigens, insulin and other key proteins associated with beta cell functions.

#### 4.4 Autoreactive T cells in T1D

As reviewed in Wong 2008, many studies carried out in the NOD mouse model of T1D have indicated that both CD4+ and CD8+ T-cells inflict islet  $\beta$ -cell damage both at an early stage in diabetes development and at the final effector phase (26-28). There appears to be considerable similarity between the antigens recognized in humans and in the NOD animal models. In human studies, so far limited to testing peripheral blood lymphocytes, a variety of reactivities to putative autoantigens have been found, including proinsulin, GAD65, pPIAPP (pre-pro-islet amyloid polypeptide protein) and GFAP (glial fibrillary acidic protein). By the time diabetes occurs, it appears that there may be a broad spread of reactivity, which is different for each subject, and it will continue to be a major challenge to identify those antigenic epitopes that are important in the early phases of pathogenesis. Many of these antigenic epitopes represents attractive targets to go after for T1D therapeutic interventions.

Mechanisms by which T cells cause damage include production of cytotoxic cytokines such as IFN $\gamma$  (interferon  $\gamma$ ) and TNF $\alpha$  (tumour necrosis factor  $\alpha$ ), that have a direct cytotoxic action on the islets. In addition, these cytokines have an important role in up-regulation of MHC class I molecules, which could increase immune recognition of the cells. These T-cell-generated inflammatory cytokines can work together with cytokines produced by macrophages, such as IL (interleukin)-1, to have a synergistic damaging effect on islet  $\beta$ -cells. The CD8+ CTLs also exocytose granules from secretory lysosomes which contain cytotoxic proteins that include the pore-forming protein, perforin, and serine esterases, called granzymes. In summary, autoreactive T cells are considered as emerging targets for prospective antigen- specific therapeutic interventions.

#### 4.5 Immunotherapeutic approaches to treat T1D

Many broad based immunosuppressive and antigen-specific immunoregulatory therapies have been and are currently being evaluated for their utility in the prevention and treatment of T1D. These may be administered as monotherapies or in combination. Some of the below-mentioned have shown efficacy in initial clinical trials. Many tend to be small molecule inhibitors and monoclonal antibodies directed against cytokine and cytokine receptors, proteases, CD3 or CD20 receptors (i.e. Rituximab), GAD65, CTL14, heat shock proteins, or insulin-related molecules (29). Systemic non-antigen specific immunomodulator interventions include cyclosporine A, azathioprine, and anti-thymocyte globulin (ATG) plus prednisolone.

Other cell therapies using dendritic cells are also currently being tested as described briefly below. Additional examples of cell therapies include targeting regulatory T cells (Tregs). Approaches to

isolate and expand polyclonal and antigen-specific Tregs *in vitro* have been developed for immunotherapy and a clinical trial to test this hypothesis in the US (47)

Unlike those small molecule therapies and any currently tried cell-based therapies, AVT001 provides for a potential new type of cell-based therapeutic approach to treat and/or prevent T1D. AVT001, used as a vaccine, it may activate and correct the defective regulatory pathway mediated by HLA-E restricted CD8+ T cells in the identified subjects that normally function to selectively control the pathogenic self-reactive T cells that destroy  $\beta$  cells without damaging the normal on going anti-infection and anti-tumor immunity, a process called self-nonsel discrimination (19, 20, 22, 23).

#### 4.6 Dendritic cell based therapies for T1D

Dendritic cells (DCs) were first described by Ralph Steinman (30) nearly forty years ago. It is known that DCs existed in all lymphoid and most non-lymphoid tissues. DCs are antigen-presenting cells (APCs), which play a critical role in the regulation of the adaptive immune response. To perform this function, DCs are capable of capturing antigens, processing them, and presenting them on the cell surface along with appropriate costimulation molecules. The crucial function of DCs falls broadly into two categories, each of which involves antigen presentation. The first category of DCs function is antigen presentation and activation of T cells. The second category of DCs function has been suggested that a different class of DCs exist with the function of inducing and maintaining immune tolerance.

Cell therapy using dendritic cells use “immature” dendritic cells that are *in vitro* derived from monocyte precursors isolated from diabetic subjects and then either modified with and re-injected into the same individuals with the hope of resetting the immune system balance in the individual. There is a great deal of interest in how DCs might be exploited as a form of immunotherapy. DCs are being studied as adjuvants for vaccines or as a direct therapy to induce immunity against cancer. Human clinical trials are ongoing to use DCs to induce immunity to antigens against prostate cancer, lung cancer, melanoma and multiple myeloma etc. The first attempt to use DCs as cancer vaccines in humans was made by Edgar Engleman and Ronald Levy (31), who isolated DCs from subjects with non-Hodgkin's lymphoma who had failed conventional chemotherapy, loaded the cells with immunoglobulin idiotype obtained from the subject's tumor, and re-injected the antigen-loaded cells back into the subjects. Four subjects involved in this pilot clinical trial and all treatments were well tolerated, no significant side effects were associated with the infusion of antigen-loaded DCs. Since then, pilot clinical trials of antigen-pulsed DCs have been conducted in various types of cancer, including melanoma, prostate cancer, multiple myeloma, and non- small cell lung cancer. DC-based therapy as immunotherapy is also tried in human type 1 diabetes and a clinical trial to test this hypothesis has finished its phase I study in the US (Clinical Trials. gov identifier NCT00445913) (32). In general, it is widely accepted that DC-based therapy is consider a very safe therapy.

#### 4.7 Dosing Rationale

Our preclinical human *in vitro* studies and murine *in vivo* studies formed the scientific basis for this clinical application to assess AVT001 *in vivo*. AVT001 is the study product name for autologous immature dendritic cells loaded with the synthetic oligopeptide from Hsp60sp. The study product represents an individualized preparation of autologous immature dendritic cells, derived by culture of the subject's adherent primary monocytes with GM-CSF and IL-4 for 6 days, and loaded passively with the synthetic oligopeptide from Hsp60sp (QMRPVSRLV). In this study design

described in this protocol, three vaccines will be administered every 30 days (+/- 7 days but at least 21 days apart).

We feel strongly that the selection of the proposed route of administration, dose levels, dosing regimen, timing of vaccination relative to disease state, etc. in our clinical trial should rely on the information from similar human clinical trials rather than from animal studies. Particularly, it should not be heavily dependent on NOD/T1D model, which is a spontaneous disease animal model involving multiple mechanisms other than Qa-1 restricted CD8+ T cells and may not be exactly the same as human T1D subjects that we plan to test. For example, the subjects we propose to test are clearly defined to be the new onset T1D subjects who have the defect of the HLA-E restricted CD8+ T cells and the defect can be corrected *in vitro* by retriggering with AVT001. This design is based on the studies from human T1D subjects and its clinical regimen cannot be exactly mimicked and represented by the studies from NOD/T1D model. The best example in this case, which is almost identical to our circumstances is an iDC based therapy on T1D subjects (48) (32) versus its preclinical studies on NOD/T1D model (33), in that injections of  $10 \times 10^6$  iDC every 2 weeks for total four times in humans versus a single injection of  $2-3 \times 10^6$  iDC in NOD mice.

In NOD mice we have used  $0.5-2 \times 10^6$ /mouse without any abnormality in protected mice, which dose range would be proportionally about  $50-100 \times 10^6$ /person in humans. However, in search for the information in other similar human clinical trials, the dosage range used has been reported to be between  $2-50 \times 10^6$ /dose every 2 weeks from two to 13 doses and showed no significant side effects (see Table below). Particularly, in one recently completed trial using iDC on T1D subjects,  $10 \times 10^6$  iDC every 2 weeks for total four times were used (32), which is very close to our proposal, eg,  $10 \times 10^6$  iDC every 4 weeks for total three times will be used. Finally, from our own studies, HLA-E restricted CD8+ T cells represent a very potent subset of CD8+ T cells, probably account for 1-2% of total CD8+ T cells. We calculate if the iDCs needed to activate such CD8+ T cells is at a ratio of 1:50-100,  $10 \times 10^6$  of iDC would activate  $500-10,000 \times 10^6$  of HLA-E restricted CD8+ T cells, which is in the range of 1-2% of total  $10 \times 10^{12}$  CD8+ T cells.

**Table 1: Summary of dosage and route of administration of dendritic cell-base vaccines in completed human clinical trials, which have been concluded as safe therapies**

Therapy to	Dose/schedule	Route	Number Subjects	Ref
NHL (Non-Hodgkin's lymphoma)	$2-17 \times 10^6$ / 4 weeks $\times 4$	i.v.	35	(34)
	$2-17 \times 10^6$ / 4 weeks $\times 4$	i.v.	10	(31)
Melanoma	$5-50 \times 10^6$ / 2 weeks $\times 4$	i.v./i.d./i.n.	28	(35)
	$5-50 \times 10^6$ / 2 weeks $\times 4$	i.v.	14	(36)
	$3 \times 10^6 + 6/12 \times 10^6$ / 2 weeks $\times 5$	i.d.+i.v.	13	(37)
Myeloma	$0.5-11 \times 10^6$ / 4 weeks $\times 2$	i.v.	12	(38)
	$3.5-89 \times 10^6$ / 2 weeks $\times 3$	i.v.	6	(39)
Prostate cancer	$1-20 \times 10^6$ / 6-8 weeks $\times 4-5$	i.v.	51	(40)

	$10 \times 10^6$ / 2 weeks $\times$ 4	i.v.+i.d.	8	(41)
	$0.3-40 \times 10^6$ / 4 weeks $\times$ 2	i.v./i.d./i.l.	21	(42)
	$10 \times 10^6$ / 2 weeks $\times$ 3	i.v.+i.d.	13	(43)
	$0.94-2.02 \times 10^8$ / 4 weeks $\times$ 3	i.v.	14	(44)
RCC (Renal cell carcinoma)	$5-10 \times 10^6$ / 4 weeks $\times$ 3-13	i.v./i.d.	35	(45)
	$10-50 \times 10^6 + 10 \times 10^6$ / 2 weeks $\times$ 3	i.v.+i.d.	10	(46)
Type 1 diabetes	$10 \times 10^6$ / 2 weeks $\times$ 4	i.d.	10	(32)

Based on the information from our own studies and the published results from clinical trials on DC-based therapies we have chosen a relatively low dose and regimen of AVT001 for safety consideration with a maximum potential for efficacy *in vivo* in our proposal.

We choose to vaccinate newly diagnosed T1D subjects that will be determined to have the defect of HLA-E restricted CD8+ T cells and the defect could be corrected by co-culture with AVT001 *in vitro*.

According to a 2017–2018 National Health Interview Survey (NHIS), National Center for Health Statistics, and Centers for Disease Control and Prevention report, as of 2018 an estimated 187,000 children and adolescents younger under 20 years of age had been diagnosed with type 1 diabetes (49). Following the DSMB review of the safety data for the first 6 staggered adult subjects (18 years and older), no safety concerns were identified. Therefore, due to the safety established thus far and due to the high prevalence of disease in adolescents, this protocol is being amended (Amendment # 3) in a step-wise fashion to reduce the lower limit of age for eligibility to age 16.

## 5 Study Objectives and Design

Our working model for maintenance of T cell self-tolerance holds that a subset of HLA-E restricted regulatory CD8+ T cells that specifically recognize the target structure of Hsp60sp associated with HLA-E expressed on the pathogenic self-reactive T cells and selectively down-regulate these pathogenic T cells which are responsible for autoimmune diseases (19, 20, 22, 23). The failure of this HLA-E-restricted CD8+ T cell subset to recognize, or to suppress, its target population results in a permissive state in which organ-specific autoimmunity can emerge. We have identified defects in this CD8+ T cell system among nine of ten T1D subjects evaluated, and found the defect to be reversible in most of these *in vitro* by co-incubation with the synthetic oligopeptide from Hsp60sp-loaded autologous immature dendritic cells (AVT001).

### 5.1 Primary Outcomes

[figure not shown]
- To determine the safety and tolerability profile of three monthly doses of AVT001 (as compared to placebo) in subjects with T1D.

### 5.2 Secondary Outcomes

- To determine whether, among T1D subjects with *in vitro*-reversible defects in the CD8+ T cell regulatory system, infusion of AVT001 will lead to an *in vivo* reconstitution of this system.
- To determine whether, among T1D subjects with *in vitro*-reversible defects in the CD8+ T cell regulatory system, infusion of AVT001 will result in amelioration of  $\beta$  cell destruction as defined by preservation of stimulated C-peptide.

### 5.3 General Study Design

This is a double-blind, randomized, placebo-controlled study to evaluate the safety and tolerability of AVT001 cell-based therapy, and to assess its potential efficacy for the treatment of type 1 diabetes (T1D). A brief overview of the trial design is outlined in a schematic form in Figure 1.

**Figure 1: Study Design Schematic (Protocol AVT001-T1D-01)**

The trial will involve approximately 24 new-onset T1D subjects who have been identified as having: (a) a defect in HLA-E-restricted CD8+ T cell function putatively associated with pancreatic  $\beta$  cell destruction and (b) evidence that this defect of HLA-E-restricted CD8+ T cells can be corrected by *in vitro* exposure to AVT001.

Participants will be randomized, in a 2:1 ratio (AVT001:Placebo) to receive AVT001 or placebo by intravenous infusion.

- AVT001: 16 subjects to receive AVT001 through i.v. administration.
- Placebo: 8 subjects to receive saline through i.v. administration.

Subjects will be treated with 3 consecutive doses of AVT001, administered with one month (+/- 7 days) intervals between doses. The primary time point for assessment will be 3 months post-last dose (Month 5), with longer-term follow-up through Month 24.

Administration of AVT001 will be performed in a double-blinded fashion as follows: the dosage regimen will be between  $7 \times 10^6$  and  $10 \times 10^6$  cells cells/infusion for each of the three infusions 30 (+/- 7) days apart. Each infusion will be administered by qualified clinical personnel in an established clinical research facility.

Subjects will be monitored for physical or reported symptoms as well as for vital signs (including temperature, heart rate, blood pressure, and arterial oxygen saturation) throughout the infusion procedure and for a minimum of 2 hours following the procedure. Although unlikely to be required, the clinical facility will include at the subject's side all medications and equipment necessary to treat cytokine release syndrome, acute anaphylactoid/infusion reactions, respiratory distress, and cardiac arrhythmia.

A placebo control arm using saline and DMSO is being used as the comparator.

 Amendment # 3 includes participants aged 16 and older.

## 5.4 Study Duration

There are three pre-defined periods in this study.

- Screening and cell collection period will last up to 3 months
- Treatment period will consist of 3 doses, ~30 days apart (Baseline, Month 1, Month 2) and a 1-month post-last dose assessment period (through Month 3). Thus, the treatment period is defined to be 3 months in duration.
- Post-Treatment Follow-up Period will extend 21 additional months (and thus through Month 24 of the study).

## 5.5 Subject Enrollment

The justification for the study design derives from the primary outcome of the proposed trial to assess the safety and tolerability of this therapy. This is a first time in man study and therefore exposure will be managed using a staggered enrollment that will allow for review of each subjects outcomes following the initial IV. This staggered enrollment and dosing for the first 6 subjects treated will be performed as follows:

- The second subject will be treated (dosed) only after the first subject has completed through the Month 1 safety visit and the Investigator and Medical Monitor have reviewed those data.
- Treatment (dosing) of subsequent subjects will be managed in a similar fashion, with subjects treated at a rate of one subject per month, with Investigator and Medical Monitor review of the Month 1 safety and tolerability outcomes for each subject before treatment of the subsequent subject is performed.

This will continue through the 6th subject. Assuming an acceptable safety and tolerability profile is observed, enrollment of the remaining subjects will be determined by the sites accrual rate.

## 5.6 Data Safety Monitoring Board (DSMB)

A DSMB will be established that will monitor subject safety as well as data quality and adherence to safety rules. Additionally, the DSMB will review all safety/toxicity data for the trial and recommend trial modifications, suspension or termination, as needed.

The DSMB will meet after 3, 6 and 15 subjects have received at least one dose of double-blind study medication and have completed their in-clinic visit through at least one month post-dose. The DSMB will review *unblinded* data to assess the safety and tolerability of the treatments given. The DSMB will, following each of these meetings, provide the Sponsor with a summary of their findings and recommendations (if any) for protocol amendments.

A DSMB Charter will be written, to include details regarding meeting frequency, format, and membership.

### 5.6.1 Stopping Rules

Subjects will be clinically evaluated for evidence of toxicity from  $\geq$  grade 3 toxicity as determined by CTCAE which is unmanageable, unexpected and (possibly, probably or definitely) related, and attributable to protocol therapy. Termination of enrollment would be considered with 2 dose limiting toxicities (DLTs) in the first 6 evaluable subjects and 3 in the first 9 evaluable subjects. In the event of a DLT for a given subject, doses will be discontinued, the subject clinically evaluated, and taken off study. The study will be stopped for DLT resulting in death of a subject.

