### **6.3 Early Withdrawal of Subjects**

If a subject is discontinued from the study prematurely, the Investigator must select the primary reason for discontinuation on the End of Study eCRF. In addition, every effort should be made to complete the assessments listed under the “Early Term” column on the Schedule of Events.

Subjects withdrawn from the study will be considered evaluable for statistical assessment.

A subject may be removed from the study for the following medical or administrative reasons:

- Adverse Event: If a subject experiences an adverse event that the subject finds unacceptable or that, in the judgment of the Investigator or the Medical Monitor presents an unacceptable consequence or risk to the subject, the subject may be discontinued from further participation in the study.
- Administrative Discontinuation: After consultation with the Investigator or Medical Monitor, a subject may be discontinued from the study for failure to comply with protocol requirements. All instances of noncompliance must be documented in the eCRF.
- Refusal of Assessments: If for any reason, following dosing, the subject refuses further assessment during the study, the subject shall be discontinued from the study and the reasons for refusal documented. Reasonable efforts shall be made to monitor the subject for adverse events following such discontinuation. Such efforts shall be documented.

Standard supportive therapy will be maintained for subjects withdrawn from active treatment. Every effort will be made to collect safety data from these subjects through the end of study.

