#### **8.3.1 Study Days 1, 30 ± 7 days, and 60 ± 7 days**

On the first study day, a 4-hour Mixed Meal Tolerance Test (MMTT) will be performed as part of baseline evaluations. The meal test will be performed in the morning after an overnight fast, with no food or drink (with the exception of water). At the outset, a mixed meal, consisting of High Protein Boost will be administered. Blood samples for C-peptide and glucose will be collected at the following timepoints (in minutes, relative to administration of the mixed-meal): -10, 0, 15, 30, and then at 30 minute-intervals until the last time point of 240 minutes.

1-2 days prior to each study day, study personnel will contact the subject to confirm that they remain in generally good health and that there are no symptoms of acute illness.

Prior to dosing on Study Day 1, a review of eligibility should be performed and confirmed. If, prior to dosing, a randomized subject is not suitable (ineligible) for the trial, that subject will be considered a “randomization failure” and will be replaced.

The following procedures will be performed prior to study drug administration on each dosing day:

- Any changes to medical history including prior treatment, current medicines, and drug

- Focused physical exam including blood pressure, pulse, temperature and weight.
- Laboratory studies including:
  - CMP
  - CBC w diff
  - HbA1c
  - Urine MicroAlbumin panel
  - CrCl (calculation)
- 
- Measurement of auto-antibodies, including:
  - Insulin associated aAb (IAA)
  - Insulinoma associated protein 2 (IA-2, previously known as ICA-512)
  - Glutamic acid decarboxylase (GAD65)
  - Zinc transporter 8 (ZnT8).
- A urine pregnancy test will be collected for females of child-bearing potential.
- Any severe hypoglycemic events occurring since the prior study visit will be recorded. Note that non-severe events are not being collected in the database in this study, but will be monitored by the investigator, consistent with the site's standard of care.

Study drug will be administered during these visits. Laboratory data will be collected prior to initiation of the infusion of study drug.

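### The *unmanageable* condition in the stopping rule leaves a treatable related grade 3–4 infusion reaction outside the DLT counts and leaves re-dosing after it to judgement

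*Combined protocol and SAP*

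**What the plan says.** All protocol references are to Amendment 3 unless stated.

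- **Qualifying toxicity (5.6.1).** The toxicity must be CTCAE grade 3 or higher and one "which is unmanageable, unexpected and (possibly, probably or definitely) related, and attributable to protocol therapy". The next sentence turns to DLTs. No sentence states that a DLT is defined this way, but Amendment 3 has no other DLT wording.
- **Counts (5.6.1).** "Termination of enrollment would be considered with 2 dose limiting toxicities (DLTs) in the first 6 evaluable subjects", and likewise with 3 in the first 9.
- **Individual subject (5.6.1).** After a DLT, "doses will be discontinued, the subject clinically evaluated, and taken off study".
- **Death (5.6.1).** "The study will be stopped for DLT resulting in death of a subject".
- **Foreseen reactions (5.3).** The facility must have at the subject's side the medications and "equipment necessary to treat cytokine release syndrome, acute anaphylactoid/infusion reactions, respiratory distress, and cardiac arrhythmia".
- **Other adverse events (6.3).** If the subject finds an event unacceptable, or the Investigator or Medical Monitor judges the risk unacceptable, "the subject may be discontinued from further participation in the study". For withdrawn subjects, "Every effort will be made to collect safety data from these subjects through the end of study".
- **Before each infusion (8.3.1).** One to two days ahead, "study personnel will contact the subject to confirm that they remain in generally good health and that there are no symptoms of acute illness". History changes, a focused examination and laboratory tests follow on each dosing day. The eligibility review is placed on Study Day 1 only.

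**The concern.** This is a first-in-man infused cell product, each subject is planned to receive three infusions, and safety is the primary objective. The severe events most likely to follow such an infusion are acute reactions, and the protocol prepares to treat them on the spot. A reaction that is treated successfully has been managed. On the plain wording, the better the bedside care, the fewer severe related reactions count.

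Two things follow. The enrollment counts do not register such a reaction. More importantly, the only mandatory instruction to stop a subject's infusions is tied to the DLT label, so a subject with a treated related grade 4 reaction at infusion 1 could receive infusions 2 and 3 with no criterion in the protocol body to withhold them.

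The wording also affects how results are read. If a report says that no DLT occurred, that would not mean that no related grade 3+ infusion reaction occurred.

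**Working it through.** **1. Apply the wording to one case.** Take a related grade 4 reaction at infusion 1 that resolves with the treatment listed in 5.3.

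| Condition in 5.6.1 | Met? |
|---|---|
| Grade 3 or higher | Yes |
| At least possibly related | Yes |
| Unmanageable | No, it responded to treatment |
| Unexpected | Arguable (see the objection) |

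The conditions are joined by *and*, so failing on *unmanageable* alone is enough. The event adds zero to either count, and the mandatory discontinuation does not apply. Section 6.3 then governs, with *may*. The checks in 8.3.1 concern present health and state no criterion based on an earlier reaction.

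**2. Figures in the plan.** Section 5.6.1 gives no error rate or toxicity rate, so there is nothing to reproduce for this rule. The sample-size statement in 9.2 does check: 1 − 0.88^14 = 0.833, consistent with at least 80%. It concerns seeing any adverse event, not stopping.

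**3. Inputs for an illustration.** Planned AVT001 subjects: 16 (5.3). AVT001 among the first six: 4 (8.2.2). Expected AVT001 among the first nine at 2:1: 6. The rate p of a related grade 3+ infusion reaction per AVT001 subject is an **assumption**: 5%, 10% or 20%.

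**4. Re-dosing.** Section 4.7 reports that the DSMB found no safety concerns in the first six, so I look at subjects 7–24. These include 16 − 4 = 12 AVT001 subjects and 12 × 2 = 24 planned second and third infusions. Both are upper limits, because the number already dosed at Amendment 3 is not stated. The chance that at least one of the 12 has such a reaction at infusion 1 or 2 is 1 − (1 − p)^12:

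- p = 5%: 46%
- p = 10%: 72%
- p = 20%: 93%

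**5. Counts, if every such reaction counted and placebo had none.**

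| Rule | p = 5% | p = 10% | p = 20% |
|---|---|---|---|
| 2-in-6, P(X ≥ 2), n = 4 | 1.4% | 5.2% | 18.1% |
| 3-in-9, P(X ≥ 3), n = 6 | 0.2% | 1.6% | 9.9% |

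At p = 10%, with five to seven AVT001 subjects among nine (possible if later blocks are of size 3 or 6), 3-in-9 ranges from 0.9% to 2.6%. Placebo contains 10% DMSO (Table 2). If placebo had a 5% rate, the 10% column would become 8.2% and 3.2%.

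**6. Effect of the filter.** Let a fraction f of reactions pass it, so q = p × f. The chance of meeting either rule by subject 9 is P(X₄ ≥ 2) + P(X₄ = 1) × P(X₂ ≥ 2), where X₄ counts the four AVT001 subjects in the first six and X₂ the two in subjects 7–9. At p = 20%:

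- f = 1: 0.181 + 0.410 × 0.040 = 0.197
- f = 0.5: 0.052 + 0.292 × 0.010 = 0.055
- f = 0 (every reaction treatable): 0

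**7. What remained live under Amendment 3.** If the first six had no such reaction (4.7 does not say so), 3-in-9 would need all three of subjects 7–9. Two AVT001 subjects cannot supply that without a placebo event. Re-dosing is therefore the main gap.

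**The case against.** **The missing rule may exist elsewhere.** Sections 7 and 7.1 send administration and monitoring details to the operating manual, and 5.6 says a DSMB charter will be written. Neither is in the documents. This stands: only silence in the protocol body is shown. It would be wrong to infer that no rule to withhold an infusion existed anywhere.

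**The original charter had a broader pause.** The DSMB charter attached to the original protocol paused the study for any attributable grade 4 toxicity, intensive-care admission, mechanical ventilation or death, with neither filter. A similar clause in the later charter is plausible. But the old charter is superseded, names another product's infusion in that clause, and does not cover grade 3 toxicity as such.

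***Unexpected* is not empty.** Section 11.1.1 describes it for unanticipated problems, including unexpected severity, and 10.3 names only infusion-site reactions for AVT001. A severe systemic reaction is arguably unexpected. This stands, and it leaves *unmanageable* as the word that does the filtering.

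**Judgement is deliberate and others are watching.** Investigator and Medical Monitor review of the first six (5.5), DSMB review after 3, 6 and 15 subjects (5.6), 24-hour serious event reporting (11.3.1), IRB and FDA reporting (11.3.2, 11.3.3) and sponsor monitoring (11.5) can all act without a DLT. A reader might infer that a severe reaction would go unnoticed, and the documents do not support that. What these routes lack is a numerical threshold or a re-dosing criterion.

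**The percentages do not measure harm.** They give the chance that a reaction occurs at an assumed rate. Harm also needs a decision to re-dose. This stands.

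**The death stop.** A reader might infer that a related death could escape because the stop is tied to the DLT label. A fatal related toxicity is hardly manageable, and section 10.3 lists no fatal reaction as expected for AVT001, so I do not press this.

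**The SAP reports much of this.** SAP v2.0 gives severity (17.1.1), relatedness (17.1.1.2), serious events (17.1.3), discontinuations (17.1.4), dose modifications (14) and markedly abnormal vital signs (17.4). It would be unfair to say that the events are hidden. What is absent is the joint count of related, grade 3+ and infusion-reaction, which must be read from the listing in 17.1. The dedicated infusion output (17.1.6) covers local site reactions only.

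**Conclusion.** The point holds as a cheap improvement to a rule that works badly for the events it most needs to catch. It is not a failure of safety oversight. On the plain wording of 5.6.1, a treatable related grade 3–4 infusion reaction neither counts nor obliges anyone to withhold further infusions, and nothing else in the Amendment 3 body closes that gap.

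The practical weight lies in up to 24 planned second and third AVT001 infusions after subject 6. The counts matter less: they are seldom reached at modest rates, and reaching them only means that termination would be considered.

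The conclusion rests on reading the conditions as conjunctive and as the working definition of a DLT. All probabilities rest on assumed rates. Nothing in the documents shows that a severe reaction occurred or that anyone was re-dosed after one.

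**What to change.** **Wording, before reuse.** In 5.6.1 and the DSMB charter, for acute infusion-related events only (cytokine release syndrome, anaphylactoid or infusion reaction, respiratory distress, cardiac arrhythmia), remove the *unmanageable* condition and state that *unexpected* does not exclude them. Any such event of CTCAE grade 3 or higher that is at least possibly related then counts toward 2-in-6 and 3-in-9 and stops further infusions for that subject, who stays in safety follow-up, in line with 6.3. Keep both filters for other toxicities, including laboratory events. Leave the death stop as it is.

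**This trial.** SAP v2.0, section 4.2, records that the Month 5 primary analysis is done, so dosing is complete. Add one count by arm of related grade 3+ infusion reactions, with whether each subject was re-dosed, beside any statement about DLTs.

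**Cost.** A few sentences, and one tabulation from data already listed. The trigger would be met somewhat more often (the 5.2% to 8.2% shown above for 2-in-6 at an assumed 10% rate), and an affected subject would forgo up to two doses.
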